5.4.10. HBeAg Seroconversion

Seroconversion of HBeAg is defined as having achieved HBeAg seroclearance together with appearance of anti-HBe antibodies. The seroconversion of HBeAg will be summarized for the subset of participants with HBeAg positive at baseline.

Seroclearance of HBeAg is defined as (quantitative) HBeAg < LLOQ. Appearance of anti-HBe antibodies is defined as a baseline anti-HBe antibodies (qualitative) with a "NEGATIVE" result and a post-baseline assessment with "POSITIVE" result.

The seroconversion will only be assessed at the time points when the anti-HBe antibodies assessment is available. If the HBeAg value is missing at that specific time point, then the non-missing lab test closest to that specific timepoint will be used. If the non-missing lab test before and after the specific timepoint fall equidistant from the target timepoint, the later one will be used to impute the missing value.

The number and proportion of participants who achieve HBeAg seroconversion will be summarized by intervention arm and analysis phase.

In addition, the number and proportion of participants with appearance of anti-HBe antibodies but without seroclearance of HBeAg will also be summarized by intervention arm and analysis phase.

5.4.11. Time to Seroconversion

For the time-to-event endpoints described in the subsections of the following efficacy-related Sections 5.4 and 5.5, the Kaplan-Meier method will be used to estimate and plot the cumulative incidence by each intervention arm. The log-rank test will be performed to compare among the intervention arms. The median time with 90% CI will be estimated using Kaplan-Meier method. In addition, the hazard ratio and the corresponding 90% confidence interval will be estimated based on a stratified Cox's regression model by the 2 randomization stratification factors. In addition, the number and percentage of participants who had an event or were censored will be reported by intervention arm. The estimated survival curves from the stratified Cox model will be plotted for intervention arms by strata. The interaction between intervention arm and stratification factors will be explored graphically. To explore the impact of selected baseline factors in addition of study intervention, multivariate (including all baseline factors together) and univariate (each baseline factor at a time) stratified Cox models will be performed.

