1.2. Trial Design

A target of 450 adult male and female participants, 18 to 65 years of age (inclusive), will be randomized in a 2:2:2:2:1:1 ratio to one of the following intervention arms:

• Arm 1:	JNJ-3989 (100 mg) +	JNJ-6379 (250 mg qd) +	NA	(N=90)
• Arm 2:	JNJ-3989 (200 mg) +	Placebo +	NA	(N=90)
• Arm 3:	JNJ-3989 (100 mg) +	Placebo +	NA	(N=90)
• Arm 4:	JNJ-3989 (40 mg) +	Placebo +	NA	(N=90)
• Arm 5:	Placebo +	JNJ-6379 (250 mg qd) +	NA	(N=45)
• Arm 6 (control):	Placebo +	Placebo +	NA	(N=45)

NA treatment refers to entecavir (ETV), or tenofovir disoproxil fumarate (TDF), or tenofovir alafenamide (TAF). Treatment duration with JNJ-3989/placebo and/or JNJ-6379/placebo is of 48 weeks. Participants who meet the NA treatment completion criteria at Week 48 will also stop NA treatment and be monitored closely during the follow-up phase. NA treatment may be re-started at any time if protocol-defined NA re-treatment criteria will be met.

The study will be conducted in the following phases:

- Screening phase:** 4 weeks. If necessary, eg, for operational reasons, the screening phase may be extended up to a maximum of 6 weeks on a case-by-case basis and in agreement with the sponsor.
- Double-blind study intervention phase:** from Day 1 (ie, baseline) up to Week 48.
- Follow-up phase:** for 48 weeks after the end of investigational intervention. For participants who complete NA treatment during follow-up, the follow-up phase will be extended to 48 weeks after the end of NA treatment. The follow-up phase has a maximum duration of 96 weeks.

Participants will be considered to have completed the study if they have completed the assessments of the end of study visit ([Extended] Follow-up Week 48).

An Independent Data Monitoring Committee (IDMC) was commissioned for this study to monitor and review data in an unblinded manner on a regular basis to ensure the continuing safety of the study participants. The committee will meet periodically to review unblinded data, as well as the results from the interim analyses (IAs) at prespecified time points (see Section 3). A separate IDMC SAP describes details of the safety and efficacy analyses included in the IDMC periodical data reviews.

In addition, an independent Flare Expert Panel (iFLEP) was appointed for flares monitoring and adjudication. Details on the IDMC and iFLEP activities are described in their respective charter.

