For the key secondary efficacy endpoint (functional cure at week 72), the tests to compare the JNJ-3989+JNJ-6379+NA regimen against the JNJ-3989+NA and JNJ-6379+NA combination regimens, respectively, will be performed at a one-sided 0.025 alpha level. This more stringent significance level aims to support for regulatory consideration the selection of the combination regimen to be studied in confirmatory studies.

All other efficacy analyses will be based on one-sided alpha level of 0.05, and/or 90% confidence interval (CI) will be presented, with no multiplicity adjustment, unless otherwise specified.

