5.4. Other Secondary Endpoints

Statistical comparisons of all other secondary endpoints among intervention arms will be done with no adjustment for multiplicity.

In addition, the potential association between treatment outcome and baseline factors will be explored by multivariate logistic regression model in a similar fashion as described in Section 5.2.5.

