5.4.1. HBsAg Seroconversion

HBsAg seroclearance will be evaluated over all time points when assessed, with emphasis at the following time points:

- at Week 48
- at Week 96 (ie, 48 weeks after completion of all study interventions at Week 48) without restarting NA treatment,

- 12 weeks after stopping all study interventions (regardless when intervention was stopped) without restarting NA treatment, and
- 24 weeks after stopping all study interventions (regardless when intervention was stopped) without restarting NA treatment, and
- 36 weeks after stopping all study interventions (regardless when intervention was stopped) without restarting NA treatment, and
- 48 weeks after stopping all study interventions (regardless when intervention was stopped) without restarting NA treatment

Proportions at the time points listed in the above bullets will be analyzed using the Mantel-Haenszel test and 90% CIs stratified for treatment history status and screening HBeAg status.

5.4.1.1. At Week 48 and At Week 96

The proportion of participants achieving HBsAg seroclearance at EOT (Week 48), and at Week 96 (48 weeks after completion of all study interventions at Week 48) will be summarized by intervention arm. A participant will be defined as responder at Week 96 (with HBsAg seroclearance 48 weeks after completion of all study intervention at Week 48) if he/she has completed 48 weeks of treatment AND met the criteria for stopping NA treatment at Week 48 AND not required NA re-treatment between Week 48 and Week 96 AND had HBsAg seroclearance at Week 96. If the HBsAg value at Week 96 is missing, the LOCF approach will be used with the condition that no value earlier than Week 84 may be carried forward.

Those participants who did not meet the NA stopping criteria at Week 48 OR did not complete 48 weeks of treatment OR did not reach seroclearance at Week 96 will be defined as non-responders for Week 96. The participants who has no HBsAg value between Week 84 and 96 or required NA re-treatment prior to Week 96 will be considered as non-responder as well.

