5.5.3. Time to Undetectability

The following time-to-event variables will be analyzed in a similar manner as for the time to event endpoints described in the Section [5.4.11](#).

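### Time-to-event p-values come from a log-rank test with no strata named, beside hazard ratios from a Cox model stratified by both randomisation factors; the test should use the same strata and the same pairwise contrasts

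*SAP*

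**What the plan says.** SAP 5.4.11 sets one method for the time-to-event endpoints in SAP 5.4 and 5.5. It gives Kaplan-Meier curves by arm, then the test: "The log-rank test will be performed to compare among the intervention arms". It then gives the effect estimate: the "hazard ratio and the corresponding 90% confidence interval will be estimated based on a stratified Cox's regression model by the 2 randomization stratification factors". Time to NA treatment completion (5.4.3.3) and time to flare (5.4.14.2) repeat the pairing. The exploratory time-to-undetectability variables in 5.5.3 "will be analyzed in a similar manner as for the time to event endpoints described in the Section" 5.4.11, and the antibody-appearance endpoints (5.5.4.2, 5.5.5.1) also refer back to it.

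Nowhere is the log-rank test called stratified. Where the SAP tests proportions it does say so: HBsAg seroclearance rates (5.4.1) are "analyzed using the Mantel-Haenszel test and 90% CIs stratified for treatment history status and screening HBeAg status".

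On error control, SAP 5.1.1 says: "All other efficacy analyses will be based on one-sided alpha level of 0.05, and/or 90% confidence interval (CI) will be presented". SAP 5.4 adds: "Statistical comparisons of all other secondary endpoints among intervention arms will be done with no adjustment for multiplicity". Protocol 9.4.1.3 mentions only Kaplan-Meier summaries for time to seroclearance and does not settle whether the test is stratified.

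**The concern.** The log-rank test matching a stratified Cox model is the stratified log-rank test, which is that model's score test. A plain log-rank test pools participants with different underlying event rates. If the pooling factors are prognostic, the treatment contrast is diluted, and the p-value need not agree with the stratified 90% CI printed next to it.

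Both factors could be prognostic for time to NA completion. The completion criteria (SAP 5.2.1) require HBeAg negativity, and participants negative at screening are taken to remain negative, so those positive at screening face an extra hurdle. The criteria also require HBV DNA below LLOQ. Suppressed participants enter below 60 IU/mL, while untreated participants enter at 2,000 IU/mL or more, or 20,000 or more if HBeAg-positive (Protocol 5.1).

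Omitting the strata also departs from the SAP's own reasoning: its amendment history says the Wilson interval was removed because it does not account for the stratification factors.

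At stake are avoidable power loss and a possible visible conflict between p-value and interval on secondary and exploratory outputs.

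**Working it through.** **Check on the setting.** The documents give no power, event count or hazard ratio for any time-to-event endpoint, so there is no stated figure to reproduce. As a check on arm sizes and the one-sided 0.05 level, protocol Table 7 was recomputed with power = Φ[(δ − 1.645·SE0)/SE1], where SE0 is pooled and SE1 unpooled:

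- 40% vs 25%, 90/90: stated 0.699, computed 0.695
- 45% vs 25%, 90/90: 0.882, computed 0.884
- 50% vs 25%, 90/90: 0.972, computed 0.970
- 50% vs 25%, 90/45: 0.889, computed 0.889
- 25% vs 10%, 90/45: 0.686, computed 0.680

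**Inputs from the documents.** Participants "will be randomized in a 2:2:2:2:1:1 ratio to one of the following intervention arms" (90 in Arms 1 to 4, 45 in Arms 5 and 6). The aim is 40% not currently treated, of whom 40% are expected to be HBeAg-positive. That gives 0.40 × 0.40 = 16% and 0.40 × 0.60 = 24% of the total.

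**Assumptions.** The HBeAg-positive share among suppressed participants is not given. Taking 25% gives 0.60 × 0.25 = 15% and 0.60 × 0.75 = 45%. Hazards are exponential, with 4-weekly visits over 96 weeks and one-sided 0.05. Effect sizes, event rates and prognostic strength are all assumed.

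**Disagreement and type I error.** With 90 vs 45, treatment hazard ratio (HR) 1.7 and 50% control events (10,000 to 20,000 runs):

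| Prognostic strength | Unstratified power | Stratified power | Difference (points) | Verdicts differ |
|---|---|---|---|---|
| None | 71.1% | 70.5% | −0.6 | 2.8% |
| HBeAg twofold | 69.3% | 71.1% | 1.8 | 4.6% |
| HBeAg fourfold | 62.6% | 70.2% | 7.6 | 8.6% |
| HBeAg eightfold | 54.8% | 70.0% | 15.2 | 15.4% |
| Both threefold | 55.6% | 69.0% | 13.4 | 14.6% |

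Under the null with fourfold HBeAg prognosis, the unstratified test rejects 3.5% of the time and the stratified test 4.8%. The plain test is conservative.

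**Dependence on event rate.** Two hazard patterns were used. Pattern A gives HBeAg-positive participants 0.3 of the HBeAg-negative hazard. Pattern B uses multipliers 0.2/1/0.3/1.5 over the 16/24/15/45% strata. Power is shown unstratified → stratified. The low-event rows used 2,000 runs, so the Monte Carlo SE is at most √(0.25/2,000) = 0.011.

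| Control events, HR, sizes | Pattern A | Pattern B |
|---|---|---|
| 70%, 1.5, 90/90 | 0.66 → 0.75 | 0.55 → 0.73 |
| 25%, 1.5, 90/90 | 0.44 → 0.47 | 0.41 → 0.43 |
| 25%, 2.0, 90/90 | 0.82 → 0.83 | 0.80 → 0.84 |
| 10%, 1.5, 90/90 | 0.24 → 0.25 | 0.24 → 0.23 |
| 5%, 3.0, 90/90 | 0.67 → 0.67 | 0.69 → 0.70 |
| 5%, 5.6, 90/45 | 0.93 → 0.93 | 0.93 → 0.94 |

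An HR of 5.6 corresponds to 25% vs 5%: ln 0.75 / ln 0.95 = 5.6. With non-prognostic strata at 70% events, power is 0.77 unstratified and 0.76 stratified.

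The 70% row needs frequent events. Power of 0.77 at HR 1.5 takes 4(1.645 + 0.739)²/(ln 1.5)² ≈ 138 events, or 138/180 = 77% of participants.

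**Which row fits.** Protocol Table 7 assumes NA completion at Week 48 of 5% in control and 10 to 50% elsewhere. Protocol Table 8 has mean HBsAg seroclearance below 1% on NA, with a 5% benchmark. The low-event rows are the nearer ones. The 70% row could describe only commoner events, possibly HBsAg below 100 IU/mL.

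**Sensitivity.** The low-event range depends on the two patterns. With both factors prognostic at 25% control events (90 vs 45, HR 2.0), power goes from 61.7% to 67.5% if each is threefold (5.8 points) and from 53.8% to 66.6% if each is sixfold (12.8 points).

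**The case against.** A plain log-rank test beside a Kaplan-Meier plot is a defensible descriptive choice. It is valid under the null, carries no decision rule here, and sits next to a stratified estimate and survival curves by stratum that 5.4.11 already plans. The SAP never uses the word unstratified, so the reading comes from omission. All of this stands and limits the point to an improvement. The plain reading remains that the test has no strata, because the Cox model in the same paragraph is expressly given them.

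A second objection also stands. The test compares six arms. If it is one global test, adding strata will not align its p-value with a pairwise hazard ratio, and a six-arm test cannot be one-sided. The contrasts have to be named as well.

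Four stronger inferences are tempting and are not supported:

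- **That false positives increase.** The simulations show the opposite.
- **That losses of 9 to 18 points apply to NA completion or HBsAg seroclearance.** Under Patterns A and B those losses arise at about 70% control events, far from the planned rates.
- **That time to NA completion drives regimen choice.** The protocol ties dose and regimen selection to functional cure at Week 72 (9.4.1.2), and time to NA completion is not among its listed endpoints (Section 3).
- **That HBeAg strata matter for time to HBeAg seroclearance.** SAP 5.4.11.2 restricts it to participants HBeAg-positive at baseline, so in practice only treatment history can act there.

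**Conclusion.** The mismatch is real and minor. Test and estimate can give different answers, and the test is conservative and loses power where the randomisation factors are prognostic. Under Patterns A and B the loss is about 0 to 4 points at 5 to 25% control events and about 9 to 18 points at about 70%. It could exceed 4 points at 25% events if both factors were strongly prognostic. Stratifying costs at most about 1 point if neither factor matters. The direction follows from the method; the size rests on assumed hazards, event rates and strata mix. The affected endpoints are other secondary and exploratory ones without multiplicity control, so no primary or key secondary conclusion depends on this.

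**What to change.** In SAP 5.4.3.3, 5.4.11 and 5.4.14.2, specify a log-rank test stratified by screening HBeAg status and treatment history, performed for the same named pairwise contrasts as the Cox hazard ratios. For time to HBeAg seroclearance (5.4.11.2), use treatment history as the only stratum. Sections 5.5.3, 5.5.4.2 and 5.5.5.1 then follow by reference. The cost is a few words in three sections, a list of contrasts, and a strata statement in the code; no new data are needed.

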5.4.11.1. Time to HBsAg Seroconversion

Seroconversion of HBsAg is defined as HBsAg level < LLOQ. Time to HBsAg seroconversion is defined as the number of days between the date of first study intervention intake and the date of the first occurrence of HBsAg seroconversion (i.e. the date of the first HBsAg seroconversion – the date of first study intervention intake + 1). The participants who withdrew early from the study before achieving HBsAg seroconversion or who did not achieve HBsAg seroconversion will be censored at the last available HBsAg assessment.

In addition, time to the first occurrence of HBsAg <10 IU/mL (i.e. the date of the first occurrence of HBsAg <10 IU/mL – the date of first study intervention intake + 1), HBsAg <100 IU/mL (i.e. the date of the first occurrence of HBsAg <100 IU/mL – the date of first study intervention intake + 1), time to the first occurrence of HBsAg decline $\geq 2.0 \log_{10}$ IU/mL (i.e. the date of the first occurrence of HBsAg < HBsAg decline $\geq 2.0 \log_{10}$ IU/mL – the date of first study intervention intake + 1) and time to the first occurrence of HBsAg decline $\geq 3.0 \log_{10}$ IU/mL (i.e. the date of the first occurrence of HBsAg < HBsAg decline $\geq 3.0 \log_{10}$ IU/mL – the date of first study intervention intake + 1) will also be evaluated.

5.4.11.2. Time to HBeAg Seroconversion

Seroconversion of HBeAg is defined as HBeAg level < LLOQ. Time to HBeAg seroconversion will be analyzed on the subset of participants who were HBeAg 'positive' at baseline. Time to HBeAg seroconversion is defined as the number of days between the date of first study intervention intake and the date of the first occurrence of HBeAg seroconversion (i.e. the date of the first HBeAg seroconversion – the date of first study intervention intake + 1). The participants who withdrew early from the study before achieving HBeAg seroconversion or who did not achieve HBeAg seroconversion will be censored at the last available HBeAg assessment.

5.4.12. ALT Decrease and Normalization

The number and proportion of participants who achieve ALT normalization on treatment and off treatment but without restarting NA treatment will be summarized descriptively by intervention

arm and analysis phase, over time, only for the subjects who had ALT elevation ($ALT \geq ULN$) at baseline. A participant with ALT elevation at baseline achieves ALT normalization if his/her ALT value post-baseline is $< ULN$ at any given time point.

Descriptive statistics of the absolute values and changes from baseline over time in ALT will be summarized by intervention arm and study phase for those participants who had ALT elevation at baseline. An additional summary of descriptive statistics of the ALT absolute values and changes from baseline over time will be summarized by intervention arm and study phase for those participants who had ALT values within the normal range at baseline.

5.4.13. ALT Normalization After NA Re-Treatment

Proportion of participants who have $ALT \geq ULN$ before NA re-treatment and reach ALT normalization after NA re-treatment during follow-up will be summarized by intervention arm.

5.4.14. Flares

5.4.14.1. Definition

The criteria based on blood markers/lab tests for each of the flare types are defined as below.

a) Virologic flare is defined as follows:

Virologic flare will be assessed only for those participants who are off-treatment and had HBV DNA < LLOQ at the last observed time point on all study treatments.

The start date of a confirmed virologic flare is defined as the first date of two consecutive visits with HBV DNA > 200 IU/mL. The end date of the same confirmed virologic flare is defined as the first date when HBV DNA value returns to \leq 200 IU/mL or the date of treatment restart, whichever comes first. Each virologic flare will be categorized based on the confirmed (i.e., two consecutive values) peak HBV DNA above any of the three thresholds within the start and end date of that flare as follows: 20,000 IU/mL 2,000 IU/mL and 200 IU/mL.

- 1 (Yes) = confirmed** HBV DNA > peak threshold.
- 0 (No) = at least one off-treatment HBV DNA measurement available and not meeting the criteria of confirmed HBV DNA > peak threshold.
- 2 (Not applicable) = no off-treatment HBV DNA quantitative measurements available.

b) Biochemical flare is defined as follows:

- 1 (Yes) = confirmed** ALT and/or AST \geq 3x ULN and \geq 3x nadir (ie, lowest value observed up to the start of the flare)
- 0 (No) = otherwise

The start date of a confirmed biochemical flare is defined as the first date of two consecutive visits with ALT and/or AST \geq 3x ULN and \geq 3x nadir. The end date of the same confirmed biochemical flare is defined as the first date when there is a 50% reduction from the peak ALT and/or AST level & $<$ 3x ULN.

c) Clinical flare is defined as follows:

Clinical flare will be assessed with both derivations specified above for virologic flare.

- 1 (Yes) = confirmed** HBV DNA > peak threshold and confirmed** ALT and/or AST \geq 3x ULN and \geq 3x nadir (ie, lowest value observed up to the start of the flare).
- 0 (No) = otherwise

A clinical flare occurs when a virologic flare and biochemical flare overlap in time. However, if there is no overlap in time, a clinical flare occurs when a virologic flare ends prior to a biochemical flare starting, and the end date of the virologic flare is within 4 weeks of the biochemical flare start date. The start date of a clinical flare is defined as the minimum start date of the virologic flare and the biochemical flare. The end date of a clinical flare is defined as the maximum end date of the virologic flare and biochemical flare, e.g., the later date of HBV DNA ≤ 200 IU/mL and 50% reduction from the peak ALT and/or AST level & $<3x$ ULN.

** Confirmed means that the criterion should be fulfilled at 2 or more consecutive time points or at the last observed time point.

The virologic and clinical flares will be assessed only off-treatment, while biochemical flares will be identified on treatment and off treatment, respectively. On-treatment virologic flares are described as virologic breakthrough in Section 5.4.15.1. On-treatment will be defined as the time period in which the participant receives any of the study interventions. Off-treatment will be defined as the time period after stopping all study interventions (including NA).

The incidence rate will be calculated and summarized for each type of on-treatment or off-treatment flares (virologic, biochemical and clinical) separately, as well as the overall incidence of participants experiencing at least one flare, regardless of type, by study intervention arm. Additionally, for each participant the total number of flares the participant experienced will be counted by type and overall, respectively. Such counts will be used to summarize the distribution of the total number of flares both by type and across types by intervention arm.

For on-treatment biochemical flares, the incidence of flares causing treatment discontinuation will be summarized by intervention arm. Further, for off-treatment flares, the count and percentage of participants who experienced a flare followed by NA re-treatment will be summarized by flare type and intervention arm. Similarly, the incidence of flares followed by the achievement of HBsAg seroclearance (at any time) will be summarized by flare type and intervention arm.

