At regular time points throughout the study (see Schedule of Activities), blood samples for biochemistry, blood coagulation, and hematology and urine samples for urinalysis, urine chemistry, and renal biomarkers will be collected. Vital signs (systolic and diastolic blood pressure [SBP and DBP], pulse rate, and temperature), height (at screening only), weight, and electrocardiograms (ECGs) will be recorded throughout the study. Physical examinations will be performed and AEs will be assessed (see Section 8.2, Safety Assessments). Events of Special Interest will be closely monitored (Section 8.3.6, Specific Toxicities).

An Independent Data Monitoring Committee (IDMC) and an Independent Flare Expert Panel (IFLEP) will be established for continuous monitoring of SAEs, AEs leading to discontinuation, and ALT flares to ensure the continuing safety of the participants enrolled in the current study (see Section 9.5, Interim Analyses).

Participants who meet the individual participant NA treatment completion criteria (Section 6.6) will be monitored for 48 weeks after completing NA treatment with frequent follow-up visits and pre-defined re-treatment criteria (Section 6.7).

The post-treatment monitoring and NA re-treatment criteria were further updated based on findings from a case of post-treatment HBV reactivation with subacute hepatic failure and assessment of additional REEF-2 study data (Section 6.7).

JNJ-3989 will be administered using a proper subcutaneous technique to decrease the risk of ISRs. ISRs will be managed as outlined in Section 8.3.6, Specific Toxicities.

Any clinically significant abnormalities persisting at the end of the study/early discontinuation will be followed-up by the investigator until resolution (return to baseline) or until stabilization (to be agreed upon with the sponsor).

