6.7. NA Re-treatment Criteria and Monitoring After Stopping of NA

Participants who meet the NA treatment completion criteria outlined in Section 6.6 will be monitored closely during the follow-up phase.

After stopping NA treatment, participants should be monitored as follows:

- Regular monitoring visits will be every 4 weeks during the follow-up phase in accordance with the Schedule of Activities.
- A post-treatment HBV DNA value of >20,000 IU/mL should trigger re-testing of ALT/AST, HBV DNA, and total and direct bilirubin within a maximum of 7 days from receipt of the data and further repeats as necessary (ie, weekly until HBV DNA returns to <20,000 IU/mL).
- A post-treatment HBV DNA value of >2,000 IU/mL (but <20,000 IU/mL) should trigger a re-test within 14 days from receipt of the data and further repeats as necessary (ie, every other week until HBV DNA returns to <2,000 IU/mL).
- A post-treatment ALT value of >5x ULN should trigger re-testing of ALT, AST, ALP, total and direct bilirubin, INR, albumin, and HBV DNA on a weekly basis until ALT and AST levels have returned to <5x ULN.

After stopping NA treatment, participants should re-start NA treatment:

- Immediately with signs of decreasing liver function based on laboratory findings (eg, INR, direct bilirubin) or clinical assessment (eg, ascites, hepatic encephalopathy).
- Immediately with an HBV DNA value of >100,000 IU/mL (irrespective of confirmation and/or ALT increase).
- With confirmed post-treatment HBeAg seroreversion (HBeAg positive after it was negative at NA completion).
- With confirmed* post-treatment increases in HBV DNA >2,000 IU/mL and ALT >5x ULN.
- With confirmed* post-treatment increases in HBV DNA >20,000 IU/mL.

Note: Additional re-testing and/or earlier restarting of NA treatment is at the investigator's discretion, even if the above cut-offs are not yet met.

To avoid delays in decision making, sites are encouraged to run local re-testing in parallel with central re-testing in the situations described above that require more frequent re-testing. Local test results are to be recorded in the CRF and/or source documents, including information on the HBV DNA assay used. In addition, to avoid delays in NA re-treatment, it should be considered to dispense NA to participants who potentially met the NA re-treatment criteria (eg, pending confirmation) and who will not be available to come to the study site immediately at the time the

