3.2. Independent Flares Monitoring

Flares in this study will be adjudicated by the independent FLares Expert Panel (iFLEP). The iFLEP flare adjudication results are sent to the IDMC Chairperson, and the information will include conclusions and review history for each flare. Additional details are provided in the iFLEP Charter document. Flares are defined in Section [5.4.14](#).

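### SAP 5.4.14.1 gives two conflicting meanings of a confirmed flare; under one of them, a rapid off-treatment HBV DNA rise that ends in immediate NA re-start is under-graded or not counted

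*SAP*

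**What the plan says.** SAP 5.4.14.1 sets out four elements for virologic flares after all study interventions, including NA, have stopped.

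- **Start:** "the first date of two consecutive visits with HBV DNA > 200 IU/mL".
- **End:** return to 200 IU/mL or below, "or the date of treatment restart, whichever comes first".
- **Grade:** thresholds of 200, 2,000 and 20,000 IU/mL, with the flare "categorized based on the confirmed (i.e., two consecutive values) peak HBV DNA above any of the three thresholds within the start and end date".
- **Period:** "The virologic and clinical flares will be assessed only off-treatment".

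The line that codes a flare as present cites a footnote: "Confirmed means that the criterion should be fulfilled at 2 or more consecutive time points or at the last observed time point". A participant with at least one off-treatment value who does not meet the criterion is coded as no flare, not as missing.

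Protocol 6.7 lists among its re-start rules: "Immediately with an HBV DNA value of >100,000 IU/mL (irrespective of confirmation and/or ALT increase"). Signs of decreasing liver function also lead to immediate re-start.

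**The concern.** The start-date and grading sentences ask for two values. The re-start rule can end the off-treatment period after one. The second value is then drawn on NA, after the flare window has closed. The footnote could cover this, but the start-date sentence omits its alternative, the gloss on the peak contradicts it, and its last time point is not tied to any period. Two programmers could classify the same participant as no flare and as top category.

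Frequency of flares is a secondary endpoint. The classification also feeds clinical flares (which need a virologic flare), time to off-treatment flare, and the table of flares followed by NA re-treatment. Any error runs towards understating severity after NA is stopped. Protocol 2.3.3 says the monitoring and re-treatment criteria were updated following "a case of post-treatment HBV reactivation with subacute hepatic failure".

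**Working it through.** The plan states no figure for this rule, so there is none to reproduce. The check has three steps.

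**1. Apply both readings to example series.** Reading A requires two consecutive off-treatment values. Reading B also accepts the last off-treatment value. The values are illustrative; NA is re-started at the last one shown.

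| Off-treatment HBV DNA (IU/mL) | Reading A | Reading B |
|---|---|---|
| 10, 150,000 | no flare | >20,000 |
| 500, 150,000 | >200 | >20,000 |
| 5,000, 150,000 | >2,000 | >20,000 |
| 50,000, 150,000 | >20,000 | >20,000 |
| 10, 150,000, then 300,000 drawn before re-start | >20,000 | >20,000 |

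Slower series without immediate re-start agree under both readings: 3,000, 4,000, 3,500 gives >2,000, and 25,000, 30,000 gives >20,000. If the footnote means the last value in the study, it does not help these cases, because follow-up continues after re-start.

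**2. How fast must the rise be?** To go from level L to 100,000 IU/mL between samples d days apart, the doubling time must be below d / log2(100,000 / L).

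| From L (IU/mL) | Effect under A | d = 28 | d = 14 |
|---|---|---|---|
| 200 | missed | 28/8.97 = 3.1 days | 14/8.97 = 1.6 days |
| 2,000 | graded >200 or missed | 28/5.64 = 5.0 days | 14/5.64 = 2.5 days |
| 20,000 | graded >2,000 or lower | 28/2.32 = 12.1 days | 14/2.32 = 6.0 days |

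The Schedule of Activities has Follow-up Weeks 2, 4, 6 and 8 and then 4-weekly visits for participants who stopped NA, so both spacings occur. Protocol 6.7 also triggers a re-test within 14 days of receiving a value above 2,000 IU/mL. With an assumed 4-day result lag, the 12.1-day limit shrinks to (14 + 4)/2.32 = 7.8 days.

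**3. Illustrative simulation under Reading A.** Assumptions: exponential rise from 20 IU/mL, onset uniform within a visit interval, 4-day result lag, re-tests as in Protocol 6.7 but no later than the next visit, NA re-started on the date of the first value above 100,000 IU/mL, and 20,000 runs. Percentages are rounded.

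| Visits | Doubling time | No flare | >200 | >2,000 | >20,000 |
|---|---|---|---|---|---|
| 4-weekly | 2 days | 36 | 24 | 24 | 17 |
| 4-weekly | 3 days | 4 | 36 | 35 | 25 |
| 4-weekly | 4 days | 0 | 19 | 31 | 50 |
| 2-weekly | 2 days | 0 | 19 | 47 | 33 |
| 2-weekly | 3 days | 0 | 0 | 50 | 50 |
| 2-weekly | 4 days | 0 | 0 | 34 | 66 |

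At a 10-day doubling time everyone is in the top category with either spacing. If a repeat sample is drawn when NA is re-started 4 days later, and that sample counts as inside the flare, everyone is in the top category at every doubling time tried.

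**The case against.** The strongest defence is the footnote. Because assessment is off treatment only, the last off-treatment value is a natural reading of the last observed time point, and every fast series then lands in the top category. That reading is available but not stated. The same section specifies a period when it means one: eligibility refers to the last observed time point on all study treatments. The peak gloss also spells out two consecutive values. So the conflict stands.

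A second defence is that the start-date sentence does not require the second visit to be off treatment. On that reading, <20 then 150,000 IU/mL could count as a flare if the next on-NA value exceeds 200 IU/mL. This weakens the claim of an outright miss. It does not repair the grading, which is confined to a window closed by re-start.

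A reader might infer that the most serious reactivations disappear from the report or from expert review. The documents do not support that, for three reasons.

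- SAP 5.4.4 lists participants who met re-treatment criteria with the criterion met, and SAP 5.4.8 counts required re-treatment as off-treatment failure. Neither source gives flare type, peak category or time to flare.
- Biochemical flares are identified on and off treatment and do not end at NA re-start.
- SAP 3.2 says "Flares in this study will be adjudicated by the independent FLares Expert Panel (iFLEP"), but Protocol 9.5.2 has that panel monitoring ALT flares, and its detailed process is in a charter that is not among these documents.

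**Conclusion.** The concern holds as a contradiction within SAP 5.4.14.1 that matters because of Protocol 6.7. Under the two-consecutive-values wording, a rapid rise ending in re-start is coded as no flare when the prior value is at most 200 IU/mL, and is graded by that prior value when it is above 200 and up to 20,000 IU/mL. A prior value above 20,000 IU/mL, or a re-test drawn before re-start, gives the correct grade.

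The size is unknown. The documents give neither doubling times nor reactivation rates, so the simulation illustrates the mechanism and forecasts nothing. Its 4-weekly rows are unfavourable for the first 8 weeks, when visits are 2-weekly, and re-start on the sampling date leaves no time for a repeat sample. During those 8 weeks few or none would be missed outright, and under-grading is the main error. A conclusion that the plan loses the fastest reactivations by design would go too far, because the footnote permits a reading that captures them.

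The importance is minor to moderate: a secondary endpoint without multiplicity control, but one that describes the main risk of stopping NA.

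**What to change.** In SAP 5.4.14.1, use one definition of confirmed for the start date, the peak category and the flare flag: two consecutive values, or the last HBV DNA value on or before the NA re-start date, with a sample taken on that date counting. Bring the gloss on the peak into line with it.

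The cost is a few sentences and reprogramming on data already collected. Some single-value spikes followed by re-treatment will count as flares. SAP 1.5 has the sponsor fully unblinded at the primary analysis, and SAP Amendment 2 refers to past interim analyses. The change would therefore be made after unblinding, so the flare tables should also be shown under the two-consecutive-values rule. No change to the clinical re-start rule is implied.
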